8.5. Esophageal Motility

- Measures LES resting pressure following standard protocol
- $> 50\%$ peristalsis with $> 30\%$ distal amplitudes
- 10 consecutive water swallows allows the assessment of propulsive motor function of the esophagus
- High-resolution motility is optional

9. Study Procedures

The schedule of observations and assessments to take place during the study follows on the next page. (**Table 4**)

Table 4. Study Events Schedule

	Initial Screening	Final Screening	Procedure	Post-Procedure/ Hospital Discharge	2-Week ±3 days	3-Month ± 15days	6-Month ± 20 days	12 and 24 Months ± 20 days
Inclusion/Exclusion Criteria	X	X						
Sign Informed Consent Form		X						
Demographics and Medical History	X							
Physical examination	X			X				
Record concomitant medications	X	X	X	X	X	X	X	
Recording of GERD Medications	X				X	X	X	X
Recording of duration of GERD Symptoms	X				X	X	X	X
Recording of type of GERD Symptoms	X				X	X	X	X
Recording of PPI Use; except for 2-week and 3-month visits, discontinue PPI usage for 7 days to evaluate study endpoints	X			X	X	X	X	X
RDQ, atypical symptom RSI, Quality of Life questionnaires GSRS, HRQL after being off PPI for at least 7 days	X						X	X
Discontinuation of anticoagulants if applicable (at least 10 days before scheduled TIF)	X							
EGD with optional biopsy		X					X	
Motility studies (High resolution optional)		X						
BRAVO pH study (at least 7 days after stopping all antisecretory compounds)		X					X	
Study Enrollment		X						
Hiatal Hernia Repair			X					
TIF 2.0 Procedure (if Hiatal Hernia successfully repaired with at least 2 cm of intra-abdominal esophagus)			X					
Adverse Event Reporting			X	X	X	X	X	

9.1. *Determination of Patient Eligibility – Screening Process*

Initial Screening -

The following pre-procedure data must be collected in order to determine patient eligibility:

- Demographics and medical history, to include age, weight, gender, and race
- Usage of GERD medication (medication, dosage, frequency and duration)
- Duration of GERD symptoms
- Type of GERD symptoms
- Duration of PPI Use
- Clinical symptom assessments (RDQ) and Quality of Life questionnaires (GSRS, HRQL, Atypical Symptom RSI)
- All general inclusion/exclusion criteria have been met

Upon completion of the Initial Screening Process, if it is determined that the patient does not have “troublesome” symptoms while on PPIs, they are **NOT eligible** for the study

Final Screening :-

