The following pre-procedure data must be collected in order to determine eligibility:

- Informed consent signing
- Physical Examination
- Days since last PPI intake (prior to BRAVO pH study)
- EGD with optional biopsy
- High resolution motility studies (optional)
- Upper GI endoscopy
- Bravo pH studies (48 hours)

Patients who have met all entry criteria are enrolled to the study.

9.2. *Prior to the Study Procedure*

- The usage of any anticoagulants will be discontinued before TIF for at least 10 days.
- 12-hours before the procedure, the patient is expected to be fasting.
- Immediately before the procedure, each patient will undergo an endoscopic examination of the stomach and esophagus.

9.3. *During the Study Procedure*

A Transoral Incisionless Fundoplication will be performed following the standard laparoscopic Hiatal Hernia Repair and closure of the diaphragmatic defect (crura closure will be made

posterior with 2-3 separate stitches). The patient will be terminated from the study if hiatal hernia cannot be repaired, with at least 2 cm intra-abdominal esophageal length.

TIF Procedure (Treatment)

The TIF procedure (treatment) will be conducted under continuous visualization following a standard TIF2.0 protocol (**Figures 8**).

[figure not shown]

Figure 8. Standard TIF2 protocol

The usage of any anticoagulants will be discontinued before HHR and TIF 2.0 for at least 10 days. Patients are expected to fast for 12 hours before the procedure. Antibiotic prophylaxis will be administered during induction of general anesthesia (oro-tracheal intubation and anti-emetic protocol; dehydrobenzoperidol, dexamethasone, Zofran, Primperan).

As stated in Section 10.2, immediately before the procedure, each patient will undergo an endoscopic examination of the stomach and esophagus. The EsophyX ZR will be inserted transorally through a bite-block into the esophagus with the patient in either in supine, or 45 degrees or left lateral position.

During a single insertion of the device, a valve similar to that created through antireflux surgery will be reconstructed by retraction of full-thickness plications and tailored placement of multiple fasteners circumferentially 1-3 cm above the Z-line. The procedure is expected to last for 30-45 minutes. The quality of the

created valve will be evaluated by an endoscopic examination immediately after the procedure. Any complications related to the procedure will be recorded.

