In the event of patient complaint of significant unmanaged GERD symptoms 14 days post procedure, the patient will be offered continued PPI therapy. (See below)

9.4. *Post-Procedure / Hospital Discharge*

Patients will be released the next day after a complete physical examination and instructed to consume a liquid diet during the first two weeks and a soft diet during the following four weeks. The liquid diet will consist of strained soups, pudding, milk, gelatin, yogurt, well-cooked and puréed vegetables, and chewable multivitamins. During weeks 3 to 6, patients will introduce a soft diet consisting of moist fish, canned fruits, bananas, berries, soft eggs, cooked vegetables, mashed potatoes, pasta, moist rice, and cereals (softened in milk). After the six-week healing time, patients can then incorporate fresh vegetables, meats, bread, citrus and alcohol back into their diet.

The usage of PPIs will be continued for 14 days following the procedure to allow healing of the gastric mucosa around the fasteners and to reduce patients' post procedure anxiety. In the event of the recurrence of troublesome symptoms, patients will be encouraged to contact the study coordinator. The nature, intensity and frequency of these symptoms will be assessed during in-office visits.

The designated staff at the clinical site will review the study requirements with the patient to maximize compliance with the follow-up schedule and the required medication regimen. Patients will be instructed to return for follow-up assessments according to the study event schedule in Section 8. A date for the follow-up visit (office or phone as appropriate) should be established between the patient and Investigator, and if possible the visits scheduled at the time of hospital discharge.

9.5. *Follow-up*

All enrolled patients will be evaluated at 2-weeks, 3-, 6-, and 12-Months and 24 months post TIF- procedure.

The study will be considered complete (with regard to the primary endpoint) after all patients have completed the 6-Month follow-up period.

Consultations may become necessary if major reflux symptoms emerge. Before each follow up time point the patient will be contacted by telephone in order to enhance clinical assessments and data compliance. Refer to the Schedule of Events (**Table 4**) for a comprehensive outline of protocol requirements.

10. Statistical Considerations

10.1. *Analysis Populations and Missing Data Handling*

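### Table 4 marks anticoagulant discontinuation at Initial Screening, before consent and the deciding eligibility tests, while sections 9.2 and 9.3 give it as a pre-procedure step; the two must be reconciled

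*Combined protocol and SAP*

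**What the plan says.** Three places in the protocol deal with stopping anticoagulants.

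- **Table 4 (section 9, Study Procedures).** The row is "Discontinuation of anticoagulants if applicable (at least 10 days before scheduled TIF". Its only mark is under Initial Screening.
- **Section 9.2 (Prior to the Study Procedure).** "The usage of any anticoagulants will be discontinued before TIF for at least 10 days". No visit is named.
- **Section 9.3 (TIF Procedure).** The rule is repeated with the same 10-day minimum, now counted back from both the hernia repair and TIF. Again no visit is named.

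Section 9.1 lists what is collected at Initial Screening, and anticoagulants are not on that list. Its Final Screening part ends with "Patients who have met all entry criteria are enrolled to the study", and 9.2 follows directly.

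In Table 4, the rows "Sign Informed Consent Form", "EGD with optional biopsy", "Motility studies (High resolution optional" and "BRAVO pH study (at least 7 days after stopping all antisecretory compounds", and the Study Enrollment row, each have their first mark under Final Screening. Section 17.5 obliges investigators to have written consent in hand before anything specific to the study is done, and section 16.3 requires it before participation.

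**The concern.** A site that works from the schedule would stop anticoagulants at the first visit. At that point the patient has not signed the consent form, and the tests that settle several entry criteria have not been done. A candidate who then fails on endoscopy, motility or acid exposure would have interrupted treatment for a procedure that does not take place.

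Sites have reason to work from the table: section 9.5 refers them to it "for a comprehensive outline of protocol requirements", and section 16.4 asks for exact adherence to the protocol.

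An event during such an interruption could also go unrecorded. Section 13 starts adverse event monitoring at enrolment, Table 4 starts adverse event reporting at the Procedure visit, and the Safety Population in section 10.1 is limited to enrolled patients who received some part of the repair or TIF. A screen failure would appear in none of these.

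**Working it through.** The plan states no figure on this point and no formula applies. The check sets the schedule beside the text.

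| Step | Table 4 | Sections 9.1 to 9.3 |
|---|---|---|
| General criteria, symptoms, history | Initial Screening | 9.1, Initial Screening |
| Anticoagulant discontinuation | Initial Screening only | 9.2 and 9.3, after the enrolment sentence; no visit named |
| Informed consent | Final Screening | 9.1, Final Screening |
| EGD | Final Screening (repeated at 6 months) | 9.1, Final Screening |
| Motility | Final Screening | 9.1, Final Screening |
| BRAVO pH, 48 hours | Final Screening (repeated at 6 months) | 9.1, Final Screening |
| Enrolment | Final Screening | 9.1, end of Final Screening |
| Hernia repair and TIF | Procedure | 9.3 |

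1. **Interval.** Table 4, 9.2 and 9.3 all give at least 10 days. There is no conflict here.
2. **Stage.** The table puts the step one visit before consent and enrolment. The text gives it under pre-procedure preparation, after enrolment has been described. The two orders differ.
3. **Consent.** Under the table's order, discontinuation comes before the only consent mark. The row ties the step to TIF, so it is done for the study procedure, and this order does not fit the duty in 17.5.
4. **Eligibility still open.** After Initial Screening, these entry criteria in section 7.1 still depend on Final Screening tests: abnormal acid exposure (inclusion 4), motility (inclusion 5), hernia size (inclusion 6, measured at endoscopy under 8.3) and esophagitis grade (exclusion 3). Any of them can still exclude the patient.
5. **Size.** The number affected would require the share of candidates on anticoagulants and the failure rate at Final Screening. The extra time off treatment would require the intervals from Initial Screening to Final Screening and from there to the procedure. The documents give none of these, and no passage sets a maximum interval.

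**The case against.** The strongest reply is that the rule does not conflict at all. The minimum is identical everywhere, and stopping at Initial Screening would also satisfy 9.2 and 9.3. The row is qualified as applying where relevant and is tied to a scheduled TIF, which does not yet exist at that visit. The mark could therefore show where anticoagulant use is identified and the instruction given. Table 4 also has no column between Final Screening and Procedure, and a mark under Procedure could not show a step due at least 10 days earlier. This may be how the mark came to stand where it does.

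Much of this stands. The agreement on interval is conceded, and the instruction reading is possible. But the row is labelled as discontinuation and no note says that the mark means anything else. Even on the instruction reading, the instruction would be given before consent.

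Two further limits stand. Some eligibility screening is done at Initial Screening: general criteria are checked, and patients without troublesome symptoms on PPIs are ruled out there. Section 9.2 also does not state that the step follows enrolment; that order comes from the sequence of the sections. The study schematic (Figure 6) is not reproduced in the text available, so whether it clarifies the order could not be checked.

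**Conclusion.** The inconsistency holds as one of study stage. Table 4 places the step before consent and before endoscopy, motility and pH testing; sections 9.2 and 9.3 present it as preparation for the procedure. It is a patient-safety and consistency point in a schedule that sites will use. It rests on reading the mark as the time of discontinuation, which is what the row label says.

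A reader might infer a stated excess of time off treatment, for instance that at least 7 + 2 = 9 days must pass between the mark and a known eligibility result (7 days off antisecretory drugs plus the 48-hour recording). The documents do not support that minimum. Table 4 already asks for the Initial Screening questionnaires after at least 7 days off PPI, so a patient who stays off, and takes no other antisecretory drug, may need only the 2 days of recording. With a procedure 8 days later (an assumption), the total is 2 + 8 = 10 days, which is exactly the stated minimum with no excess. Longer intervals are equally possible; nothing in the documents fixes them.

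A reader might also infer that every anticoagulated candidate will be taken off treatment early. That depends on how each site reads the mark. The number of such candidates is unknown, and the exclusions for ASA above 2 and for coagulation disorders may keep it small.

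**What to change.** Reconcile Table 4 with sections 9.1 to 9.3 and with the consent requirement in 16.3 and 17.5, so that all of them assign the step to the same stage. Two routes are open: a footnote to the Table 4 row saying what the mark denotes, or a corrected placement of the mark. Because the table has no column between Final Screening and Procedure, showing the step there would need a new column or a footnote. If some action is meant at Initial Screening, the list in 9.1 should name it, and its relation to consent should be stated.

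The timing is for the sponsor's clinicians to decide; none is proposed here.

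The cost is one table edit or footnote, with matching wording in section 9 if needed. The endpoint, the analysis and the power statement are unaffected.

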7.1. Selection Criteria

The table on the following pages outlines the specific inclusion and exclusion criteria for the study. Before randomization in the study, a patient must meet all of the inclusion and exclusion criteria.

Inclusion Criteria:	
1.	Age 18-80years
2.	Dependent upon daily PPIs for > 6 months. Daily use is defined as a double dose, or full dose or half dose taken daily for more than 80 % of the total number of days during the proceeding evaluation period
3.	Troublesome symptoms, specifically heartburn or regurgitation, while on optimized dose of PPI's. Troublesome heartburn or regurgitation symptoms are those which occur a minimum of 2 days a week and are mild to severe in severity.
4.	Abnormal ambulatory (Bravo) pH study after off PPI therapy for 7 days, i.e. >5.3% of the time with pH < 4 in a 48-hour monitoring period
5.	Normal or near normal esophageal motility (by Upper GI/ esophagram or manometry as required)
6.	Pre-enrollment Hiatal Hernia (axial height and transverse dimension) from > 2cm and up to 4 cm inclusive
7.	Patient willing to cooperate with post-procedure dietary recommendations and assessment tests at the requisite follow-up visits
8.	Signed informed consent
Pre-enrollment Exclusion Criteria:	
1.	BMI > 35
2.	Hiatal hernia \leq 2 and > 4 cm
3.	Esophagitis Los Angeles grade C or D
4.	Esophageal ulcer
5.	Esophageal stricture
6.	Long-segment Barretts esophagus (Prague: C > 1, M > 3)
7.	Esophageal motility disorder
8.	Pregnancy or plans for pregnancy in the next 12 months (in females)
9.	Immunosuppression
10.	ASA > 2
11.	Portal hypertension and/or varices
12.	History of previous resective gastric or esophageal surgery, cervical spine fusion, Zenker's diverticulum, esophageal epiphrenic diverticulum, achalasia, scleroderma or dermatomyositis, eosinophilic esophagitis, or cirrhosis
13.	Active gastro-duodenal ulcer disease
14.	Gastric outlet obstruction or stenosis
15.	Severe gastroparesis or delayed gastric emptying confirmed by solid-phase gastric emptying study if patient complains of postprandial satiety during assessment
16.	Coagulation disorders
17.	Symptoms including gas bloat and dysphagia.
18.	Any other presenting condition that in the opinion of the investigator would not make participation in this study in the patients best interest.
Post-enrollment Exclusion Criteria:	
1.	Inability to repair Hiatal hernia with at least 2cm of intra-abdominal esophagus length.

7.2. *Withdrawal*

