While study withdrawal is discouraged, patients may withdraw from the study at any time, with or without reason and without prejudice to further treatment. Withdrawn patients will not undergo any additional follow-up. In all cases of withdrawal, the reason(s) for withdrawal (if given) will be recorded upon study termination.

8. Study Methods and Techniques

8.1. *Clinical Symptom Assessments*

The following four GERD-specific questionnaires will be used to assess typical and atypical symptoms, their frequency and intensity, as well as their impact on daily life, relationships, quality of life, state of mind, worries and concerns, sleep and diet.

- Reflux Disease Questionnaire (RDQ)
- GERD HRQL Quality of life assessment
- GERD GSRS Quality of life assessment
- RSI Questionnaire for atypical symptoms

- The time needed for completion of all four questionnaires is estimated for 35 minutes maximum.
- A $\geq 50\%$ improvement in the total GERD-HRQL and GERD-GSRS scores compared to the baseline off PPIs will be considered clinically significant.
- A reduction in severity from \geq moderate to \leq mild and/or a reduction in frequency from ≥ 2 days per week to ≤ 1 day per week is indicative of a clinically significant result as measured by the Reflux Disease Questionnaire (RDQ).

8.2. *PPI Usage*

The use of PPIs plus other GERD medication such as histamine receptor antagonists (H2RA) and antacids will be recorded in a medication diary using generic names (**Table 3**) and classified according to the daily dose and frequency.^{18, 21}

Usage will be defined as “Daily” if a double dose, full dose or half dose is taken daily for more than 80% of the total number of days during the proceeding follow-up period.

Note: “Full Dose” is defined as the first number of mg listed for each PPI in the following table.

Table 3. Proton Pump Inhibitors (PPI)

Generic Name	Brand Names	Available Pill Sizes (mg)
Esomeprazole	Nexium	20, 40
Lansomeprazole	Prevacid, Dakar, Lando, Lanzor, Prezal, Lanzol	15, 30
Omeprazole	Prilosec, Losec, Logastric	10, 20, 40
Pantoprazole	Protonix, Zurcal, Pantozol, Zurcale	20, 40
Rabeprazole	Aciphex, Pariet	20

8.3. *Upper GI Endoscopy*

- Diagnosis of esophagitis according to the Los Angeles classification confirmed by esophageal biopsy.²²
- Hiatal hernia size will be diagnosed based on the distance from Z-line to diaphragmatic impression measured in cm at retraction of the endoscope without insufflation.

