Effectiveness Population - Per the Intent-to-Treat principle, all enrolled patients who receive the protocol TIF 2.0 procedure will be included in the effectiveness analysis.

Safety Population - Safety analysis will include all enrolled patients who receive any portion of the protocol required Hiatal Hernia Repair or TIF 2.0 procedures.

Missing data: All analyses will be based on available data. Missing data will not be imputed by methods.

10.2. *Statistical Analysis Plan*

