Study Endpoints/Outcomes	Control	Pre-procedure Value	Post-procedure Value	Success Criteria
PRIMARY EFFECTIVENESS				
Normalized acid exposure	Self-Comparison	BRAVO Ph studies after off anti-secretory meds ≥ 7 days	BRAVO Ph studies at 6 months after off anti-secretory meds ≥ 7 days	Treatment success will be defined by a proportion of TIF patients with normalized acid exposure that is non-inferior to the RESPECT result as defined in 10.2.2.
SECONDARY EFFECTIVENESS				
GERD symptoms	Self-Comparison	Reflux Disease Questionnaire (RDQ) scores	Reflux Disease Questionnaire (RDQ) scores at and 6 months	Treatment success will be defined by a proportion of TIF patients free of troublesome symptoms at 6 months that is \geq the same proportion in RESPECT Trial (67%)
PPI usage	Self-Comparison	PPI usage (must be "daily")	PPI usage at 6 months	Treatment success will be defined by $\geq 50\%$ of TIF patients that has a clinically significant reduction, i.e. from "daily" PPI use to "none" or "occasional" use, at 6 months.

12. Risks

The following risks are anticipated and can result from the TIF procedure or general anesthesia:

Expected typical risks or discomfort:

- Pharyngolaryngeal pain (e.g., sore throat)
- Musculoskeletal pain (e.g., left shoulder pain)
- Temporary epigastric or abdominal pain, which can be treated with standard pain medication
- Temporary dysphagia (i.e., difficulty swallowing) due to swelling
- Nausea or vomiting

Unusual risks or discomfort:

- Oral or dental injury
- Bleeding
- Bloating sensation
- Hematoma

Rare risks:

- Esophageal perforation, laceration or tear
- Aspiration, hypoxia, achalasia

- Nerve damage
- Arrhythmia
- Pneumothorax, chest pain
- Pneumoabdomen
- Fistula
- Infection of the mediastinal space

Additional risks:

- Operation to remove a defective device or its parts
- Reoperation after a failed procedure (insufficient symptom relief)

13. Adverse Events

All adverse events will be monitored from the time of enrolling through the 6-month follow-up visit. Unanticipated adverse device effects (UADE) and SAEs will be monitored through the 12-month follow-up.

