Patients who experience adverse events during or after the procedure will remain enrolled in the study. Once enrolled, all patients will be followed for safety and efficacy evaluations with the exception of consent withdrawals by patient.

13.4. *Device Failures and Malfunctions*

All failures and malfunctions of the study device will be documented in the electronic database, and the device will be returned to EndoGastric Solutions for analysis. Device failures and malfunctions should also be documented in the patient's medical record.

NOTE: Device failures or malfunctions are NOT to be reported as adverse events. However, if there is an adverse event that results from a device failure or malfunction, that specific event would be recorded in the usual way.

14. Data Management

14.1. *Data Collection*

Data will be collected via a standard paper-based system of CRFs. In addition to collecting data as required per this protocol, various cost and reimbursement information will be captured on a per-patient and per-site basis. All data will be treated confidentially and exported only in the aggregate non-identifiable form.

14.2. *Data Processing*

Data will be entered into a spreadsheet based database by the CRO. Visual and computer error checks will be carried out. The Investigator will be queried on errors concerning completeness and consistency.

Audits may be performed for quality assurance of the electronic database.

15. Monitoring Procedures

15.1. *Monitoring and Auditing*

Monitoring visits to the clinical sites will be made periodically during the study, to ensure that all aspects of the current, approved protocol/amendment(s) are followed. Original source documents will be reviewed for verification of data.. The Investigator/institution guarantees direct access to original source documents by EndoGastric Solutions personnel, their designees, and appropriate regulatory authorities. In the event that the original medical records cannot be obtained for a patient that is seen by a non-study physician at a non-study institution, photocopies of the original source documents must be made available for review.

The study may also be subject to a quality assurance audit by EndoGastric Solutions or its designees, as well as inspection by appropriate regulatory authorities.

It is important that the Investigator and relevant study personnel are available during the monitoring visits and possible audits and that sufficient time is devoted to the process.

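### Sections 7.1 and 9.3 terminate enrolled patients whose hernia repair fails, while 13.3 follows all enrolled patients for safety; whether adverse event collection continues for them is not stated

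*Combined protocol and SAP*

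**What the plan says.** Enrolment comes first. Under Final Screening in 9.1: "Patients who have met all entry criteria are enrolled to the study". Table 4 places enrolment in the same pre-procedure column.

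The exit rule comes in the operating room. Section 7.1 lists as a post-enrolment exclusion: "Inability to repair Hiatal hernia with at least 2cm of intra-abdominal esophagus length". Section 9.3 gives the consequence: "The patient will be terminated from the study if hiatal hernia cannot be repaired, with at least 2 cm intra-abdominal esophageal length". Table 4 makes TIF conditional on a successful repair.

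The follow-up rules are general:

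- Section 13.3: "Once enrolled, all patients will be followed for safety and efficacy evaluations with the exception of consent withdrawals by patient".
- Section 13: "All adverse events will be monitored from the time of enrolling through the 6-month follow-up visit". It also carries SAEs and UADEs to 12 months.
- Section 9.5: "All enrolled patients will be evaluated at 2-weeks, 3-, 6-, and 12-Months and 24 months post TIF- procedure".

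The analysis rules include these patients. Section 10.1 (Analysis Populations) says: "Safety analysis will include all enrolled patients who receive any portion of the protocol required Hiatal Hernia Repair or TIF 2.0 procedures". Section 10.2.3 counts events from the hernia procedure onward, tabulates repair complications, and compares the proportion of patients with medically significant adverse events with RESPECT.

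The only text on what leaving the study entails is in 7.2: "Withdrawn patients will not undergo any additional follow-up". That section is about patients who choose to withdraw.

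**The concern.** A patient whose repair fails is already enrolled and has already had surgery. Section 9.3 ends that patient's participation for a reason that 13.3 does not recognise, so the two cannot both be followed as written. The protocol does not say whether termination covers only TIF and the effectiveness assessments, or also adverse event collection.

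The stake is the primary safety hypothesis (5.4), which claims no rise over RESPECT at 6 months. Failed-repair patients belong in that result because 10.1 puts them in the safety population. If their later events are not sought, they add to the denominator and cannot add to the numerator. With three sites, practice could also differ between sites.

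**Working it through.** **Comparing the passages for one patient with a failed repair**

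| Question | Text | Answer |
|---|---|---|
| Enrolled? | 9.1, Table 4 | Yes, before surgery |
| Stays in the study? | 7.1, 9.3 | No |
| Followed for safety? | 13.3 | Yes, unless consent is withdrawn |
| Adverse events monitored to 6 months? | 13 | Yes, from enrolment |
| In the safety population? | 10.1 | Yes, any portion of the repair suffices |
| In the effectiveness population? | 10.1 | No, TIF is required |
| When are the visits? | 9.5 | Timed from a TIF that did not take place |
| Does termination end adverse event collection? | None | Not stated |

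Rows two and three conflict directly. On timing, the single Procedure column in Table 4 could serve as an anchor, but 9.5 does not use it.

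**What is lost if 9.3 is taken as the end of follow-up.** Events at the procedure are recorded on any reading. Later non-serious events have no scheduled collection. Later SAEs reach the sponsor only if the site happens to learn of them, because reporting under 13.2 starts from the site's knowledge.

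**Effect on the safety proportion.** Let N be the safety population and m the number of failed-repair patients whose only medically significant event occurs after termination and is missed. They stay in the denominator, so

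reported minus true proportion = −m/N.

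- N = 50 (the synopsis figure, if all 50 were operated on) and m = 1: 1/50 = 2.00 percentage points.
- If 50 evaluable patients are needed, as under Sample Size and Power Estimation, failed repairs come on top. With an assumed 1, 5 or 10 of them and no other losses: 1/51 = 1.96, 1/55 = 1.82 and 1/60 = 1.67 points per missed patient.
- Assumed m = 1, 3 or 5 at N = 50: 2, 6 or 10 points.

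The documents give no failed-repair rate and no event rate, so m is purely an assumption. If 13.3 is followed, m = 0 and the effect is zero.

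**The plan's own figure.** For the exact binomial rule of at least 18 of 50, with null rate 24% and true rate 44%, the one-sided alpha is 0.0384 and the power 0.9010, which agrees with the stated 0.90. A threshold of 17 would give alpha 0.0718, so 18 is correct. This test uses only patients who received TIF, so it does not depend on whether failed-repair patients have safety follow-up.

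**The case against.** The best defence is that the protocol already answers the question. Section 10.1 names these patients in the safety population, 10.2.3 counts events from the hernia procedure, Section 13 monitors from enrolment to 6 months, and 13.2 requires SAE reporting. Read together, termination most naturally means no TIF and no effectiveness data. This is probably the intent, and it is why no further statement on the safety denominator is needed. But it has to be inferred: 9.3 makes no exception for safety data, and a site that followed it literally would stop.

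A second defence is that 13.3 stands under a heading on withdrawal because of adverse events, so 9.3 could be the specific rule that prevails. That weakens the conflict without removing it. The sentence in 13.3 covers all enrolled patients, and Section 13 sets the same 6-month window independently.

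A reader might infer more: that the protocol orders safety follow-up to stop. The documents do not support this. Section 7.2 concerns withdrawal by the patient and could reach these patients only by analogy. A reader might also infer that the available-data rule removes them from the safety denominator. Section 10.1 includes them explicitly, and their procedural events are available data.

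**Conclusion.** The inconsistency is real and should be fixed. Confidence is high on the conflict of text and much lower on any resulting bias, which arises only if a site applies 9.3 as the end of follow-up.

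In that case the bias runs toward finding no increase over RESPECT, by 2 points at N = 50 for each patient whose only medically significant event is missed. The figure assumes that failed-repair patients stay in the denominator, as 10.1 provides.

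A reader might conclude that the safety finding would be reversed. That cannot be shown: the documents give no RESPECT adverse event rate, no margin and no test for this comparison.

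**What to change.** Reconcile 7.1, 9.3 and 9.5 with 13 and 13.3. State that a patient whose repair does not meet the criterion leaves only the effectiveness evaluation and, unless consent is withdrawn, remains in adverse event data collection for the windows Section 13 already sets (all adverse events to 6 months, SAEs and UADEs to 12 months). State that for these patients the windows run from the date of the hernia repair procedure. This concerns data collection only and leaves the repair criterion and patient management as they are.

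The cost is a few sentences and a few extra safety contacts for patients without TIF. The primary test and its sample size do not change.

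A separate, minor schedule correction applies to all patients. The adverse event row in Table 4 ends at 6 months, whereas Section 13 carries SAEs and UADEs to 12. Use a footnote or a split column, because 12 and 24 months share one column and a plain mark would cover both. This does not bear on the 6-month safety hypothesis.
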